5.5.2 Secondary Efficacy Analysis

The secondary efficacy endpoints include the following:

- percent of subjects with treatment success (responder on overall LFGS) at Visit 3/Month 2, where responder is defined as a subject with at least a 1-grade increase from baseline on the overall LFGS
- percent of responders on the overall POL severity scale at Visit 4/Month 3 (defined as a subject demonstrating ≥ 1 -point improvement, i.e., decrease in severity, from baseline)
- change from baseline to Visit 4/Month 3 in overall LFGS
- change from baseline to Visit 5/Month 6 in overall LFGS

The supporting importance of the secondary endpoints is ordered by [1] percent of subject with treatment success (responder on overall LFGS) at Visit 3/Month 2, [2] percent of responders on the overall POL severity scale at Visit 4/Month 3, [3] change from baseline to Visit 4/Month 3 in overall LFGS, and [4] change from baseline to Visit 5/Month 6 in overall LFGS.

These secondary variables will be summarized with descriptive statistics for each treatment arm and a 95% CI for the difference between treatments. For the proportion variables, the 95% CI for treatment difference will be calculated using the Wald's method, with subjects pooled from all study sites. For the change variables, the 95% CI for the median differences between treatments will be derived using PROC NPARIWAY with the option for the HL estimators.

For the mITT analysis, the LFGS-related secondary endpoints will be analyzed for each copy of the MI data sets. PROC MIANALYZE will then be performed to account for the between and within variation in the multiply imputed data sets.

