### 8.2 Efficacy Analysis

The primary efficacy endpoint is change from baseline to Month 2 in overall lip fullness based on the Blinded Evaluating Investigator assessment using the LFGS. A 95% confidence interval (CI) will be constructed for the difference between PN40082 and Restylane Silk (i.e. PN40082 minus Restylane Silk) with respect to the primary endpoint. If the lower limit of this 95% CI is above a pre-specified NI limit - 0.50, PN40082 will be claimed non-inferior to Restylane Silk.

The primary endpoint will also be analyzed for the following two subsets of subjects: (1) subjects that have injection on one lip only, and (2) subjects that have injections on both lips.

Secondary analysis include

- percent of subjects with treatment success (responder: overall LFGS based on the Blinded Evaluating Investigator Assessment) at Visit 3/Month 2 where responder is defined as a subject with at least a 1-grade increase from baseline on the LFGS post augmentation,
- percent of responders overall on the POL severity scale at Visit 4/Month 3 (defined as a subject demonstrating  $\geq 1$ -point improvement, i.e., decrease in severity, from baseline),
- change from baseline to Visit 4/Month 3 in overall LFGS based on the Blinded Evaluating Investigator Assessment
- change from baseline to Visit 5/Month 6 in overall LFGS based on the Blinded Evaluating Investigator Assessment.

For this non-inferiority study, the null hypothesis to be tested for all the secondary endpoints is that there is no difference between the two products, and all statistical comparisons for these endpoints will be considered descriptive (non-inferential). These secondary variables will be summarized with descriptive statistics for

each treatment arm and a 95% CI for the difference between treatments. For the proportion variables, the 95% CI for treatment difference will be calculated using the Wald's method, with subjects pooled from all study sites. For the change variables, the 95% CI for treatment difference will be derived using ANCOVA with factors of treatment and site, and the corresponding baseline value for the endpoint as covariate.

Other efficacy analysis include

- pGAI, iGAI, and Swelling Assessment at each scheduled visit,
- percent of subjects with treatment success (responder: upper lips, lower lips LFGS) at Visit 3/Month 2 where responder is defined as a subject with at least a 1-grade increase from baseline on the LFGS post augmentation,

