**Effectiveness results:**

Assessment of lip fullness included subjects with a baseline MLFS score of 1 or 2. Scoring was based on visual live assessment by the Investigator. Results of the assessment at Baseline, Week 4 and Week 12 are presented in Table 10. All subjects in the ITT population had a clinically significant improvement, i.e. at least one grade improvement from baseline for the upper lip, and the majority (49/51 [96%]) of lower lips were improved at 12 weeks.

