3.2 Sample Size Determination

For the PRO 2018-02 study, the primary variable is change from baseline to Month 3 in LFGS. The sample size was determined based on: (1) both PN40082 and Restylane Silk having an equal mean value with a common standard deviation of 0.85 for change from baseline in LFGS, and (2) the non-inferiority limit of -0.50. The test:control ratio of 1:1 results in 126 (63:63) per-protocol (PP) subjects at power of 90%. A total of 158 subjects will be randomized to obtain 126 (63:63) PP subjects assuming that 80% of randomized subjects meet the PP criteria.

4 Populations To Be Analyzed

Three subject populations are defined as follows:

- (1) As-treated (AT) (safety population): All randomized subjects who received study device. AT subjects will be included in the safety analysis for the treatment they actually received.
- (2) Modified intent-to-treat (mITT): All randomized subjects who met the inclusion/exclusion criteria, and received study device.
- (3) Per-protocol (PP): All randomized subjects who met all inclusion/exclusion criteria; received study device; completed Visit 5/Month 6 within the specified window; had overall LFGS score by the Blinded Evaluating Investigator at Visit 3/Month 2 within the specified visit window; and had no significant protocol violations that would affect the treatment evaluation.

For the purpose of determining the PP status of the subject, "significant protocol violations" are any unforeseen events that occurred during the conduct of the trial that result in noteworthy study protocol violations that could have possibly interfered with the therapeutic administration of the treatment or the precise evaluation of treatment efficacy.

Efficacy analyses will be performed on the mITT and PP populations, with PP as the primary population and mITT supportive. Analyses of safety and other evaluations will be performed on the AT population.

5 Planned Analyses

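### The Wald interval for the Month 2 LFGS responder difference is unreliable if true response rates reach about 97% and differ slightly; a score-type interval should be named before database lock

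*SAP*

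**What the plan says.** SAP section 5.5.2 lists two proportion endpoints among the secondaries: overall-LFGS response at Visit 3/Month 2 and overall-POL response at Visit 4/Month 3. For LFGS, a "responder is defined as a subject with at least a 1-grade increase from baseline on the overall LFGS". This endpoint is ranked first in supporting importance.

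For both proportions, "the 95% CI for treatment difference will be calculated using the Wald's method, with subjects pooled from all study sites". Protocol section 8.2 says the same: "the 95% CI for treatment difference will be calculated using the Wald's method". Neither document provides for sparse or boundary counts.

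The shell of Table 14.2.2.1 shows N, the number and percentage of successes, and this interval. It does so for the per-protocol (PP) population, for each of five imputed mITT data sets, and for a combined mITT row from PROC MIANALYZE. SAP section 5.1 and Protocol section 8.2 declare all secondary comparisons descriptive, and no margin is attached to either responder endpoint.

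**The concern.** The Wald interval takes its width entirely from the observed proportions. Near 100% the estimated variance shrinks towards zero, and if every subject in both arms responds the width is exactly zero.

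High response is conceivable here. The Restylane Silk Instructions for Use appended to the protocol report, for the upper lip at 12 weeks in the cannula study, that "All subjects in the ITT population had a clinically significant improvement" (meaning at least one grade), and 49 of 51 lower lips. In the present trial the lips are augmented until maximum benefit is reached, and a touch-up is allowed at Month 1, before the Month 2 assessment.

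At stake is the only between-arm statistic in Table 14.2.2.1. A reader would take (0, 0), or a very short interval, as strong evidence of equality from 63 subjects per arm.

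**Working it through.** **Inputs.** PP size is 63 per arm (SAP section 3.2). Full mITT size is at most 158/2 = 79 per arm. The documents give no assumed responder rate, so true rates of 90% to 100% are an assumption and are shown as a range.

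**The plan's own figure.** SAP section 3.2 uses "a common standard deviation of 0.85 for change from baseline in LFGS" and "the non-inferiority limit of -0.50". With two-sided 5% and 90% power, n per arm = 2 × (1.960 + 1.282)² × 0.85² / 0.50² = 60.7, so 61 by the normal approximation and 62 with the noncentral t. At 63 per arm the power is 91.0%. Then, "assuming that 80% of randomized subjects meet the PP criteria", 126/0.80 = 157.5, rounded up to 158. The stated size reproduces; it concerns the primary endpoint only.

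**Intervals at particular outcomes, n = 63 per arm.** Wald: d ± 1.96 × √[p₁(1−p₁)/n + p₂(1−p₂)/n].
- 63/63 v 63/63: the standard error is 0, so the interval is (0, 0). Newcombe uses the Wilson lower limit 63/(63 + 1.96²) = 94.25%, which gives ±5.75 points. Miettinen-Nurminen gives ±5.8.
- 63/63 v 62/63: Wald (−1.5, +4.7); Newcombe (−4.3, +8.5).
- 62/63 v 62/63: Wald ±4.4; Newcombe ±7.0.
- 57/63 v 57/63: Wald ±10.3; Newcombe ±11.0, so little changes at about 90%.

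**Exact coverage.** This sums the binomial probabilities of all outcome pairs whose interval contains the true difference. Zero width is (p₁p₂)⁶³, the chance that all 63 respond in both arms.

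| True rates, n = 63 | Wald | Newcombe | Zero width |
|---|---|---|---|
| 90% v 90% | 94.5% | 95.7% | <0.001% |
| 95% v 95% | 93.9% | 97.2% | 0.16% |
| 96% v 96% | 94.5% | 97.8% | 0.58% |
| 98% v 98% | 97.8% | 99.5% | 7.8% |
| 99% v 99% | 99.6% | >99.9% | 28.2% |
| 96% v 100% | 92.0% | 99.6% | 7.6% |
| 97% v 99% | 84.7% | 99.5% | 7.8% |
| 98% v 99% | 84.0% | 99.8% | 14.9% |
| 98% v 100% | 71.8% | >99.9% | 28.0% |

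At 79 per arm, Wald coverage is 90.3% at 97% v 99%, 86.8% at 98% v 99% and 82.5% at 96% v 100%.

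**Where the misses come from.** With equal rates, coverage stays near or above nominal. With slightly unequal rates near the ceiling, the misses are one-sided. At 97% (test) v 99% (control), 14.7% of lower limits lie above the true difference of −2 points, against a nominal 2.5%. Almost all of this is the event that the test arm is 63/63, with probability 0.97⁶³ = 14.7%. Against 63, 62 or 61 control responders the Wald lower limits are then 0.0, −1.5 and −1.2 points, all above −2.

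**Combined mITT row.** PROC MIANALYZE uses T = Ū + (1 + 1/5)B, where Ū is the mean within-imputation variance and B the between-imputation variance. An imputed data set with 100% response in both arms contributes zero to Ū. If all five are like that, B is also zero and so is T.

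**The case against.** The strongest reply is that the rates at which Wald fails may not occur. A reader might infer from the comparator label that near-100% response is likely; the documents do not support that. The 100% and 49/51 come from an open-label, single-arm cannula study. The unblinded investigator scored each lip on the MLFS at 12 weeks, only in subjects with baseline scores of 1 or 2. The present trial uses a blinded evaluator, overall LFGS and Month 2, and prohibits cannulas. The comparator's pivotal study did have a blinded-evaluator responder rate, but its values are in a figure not available here. The one Week 8 percentage visible from that study is 90.1%, for subject-rated GAIS, a different instrument.

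Eligibility also works against the ceiling. Subjects of Fitzpatrick type IV to VI with full lips (LFGS 4) may enroll and cannot gain a grade. One such subject caps that arm at 62/63 = 98.4% and rules out the all-responder result. In the arm with the lower rate, such a subject would also remove the 63/63 outcome that produces nearly all the misses at 97% v 99%. How many will enroll is not stated, so the risk is reduced by an unknown amount and not removed.

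Two further inferences go too far. Because the misses at 97% v 99% favour the test device, a reader might think the non-inferiority claim is at risk. It is not: no margin applies to this endpoint, it is declared descriptive, and the counts by arm stand beside the interval. A reader might also extend the point to POL. The documents give no numeric POL response rate, and a subject with no perioral lines at baseline cannot respond, so nothing suggests near-100% response there.

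What remains is that an interval labelled 95% can have coverage well below 95% at plausible rates, with no fallback in the plan.

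**Conclusion.** The point holds for the overall-LFGS responder difference at Month 2, at low-to-moderate severity. If true rates are about 97% or higher and differ slightly, the planned interval has 72% to 85% coverage in the three most affected cells tabulated at 63 per arm, against at least 99.4% for Newcombe, and it can collapse to zero width. Around 90% it performs adequately.

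The result assumes independent binomial responses with a common rate in each arm and does not model baseline-full subjects separately. Rates in the failing range are plausible but not shown to be likely. Only the reported precision of a descriptive secondary result is affected.

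**What to change.** Before database lock, amend SAP section 5.5.2 and the footnotes of Table 14.2.2.1:

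- **PP row and each imputed data set:** replace Wald with the Newcombe hybrid-score or Miettinen-Nurminen interval, and name which one.
- **Combined mITT row:** specify a separate method, because PROC MIANALYZE pools estimates with standard errors and a score interval does not feed it directly. Two options are a score-type interval built from the pooled proportions, or an Agresti-Caffo-adjusted estimate and standard error passed to PROC MIANALYZE. The adjusted standard error does not vanish: at 63/63 v 63/63 it gives ±4.2 points.
- **Table 14.2.2.2 (POL):** use the same interval for consistency only.

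The amendment should note that it departs from the Wald method in Protocol section 8.2. Sample size and data collection do not change. The cost is a PROC FREQ option for the single-data-set rows, a little programming for the combined row, and slightly wider intervals (±11.0 instead of ±10.3 points at 57/63 v 57/63). Choosing the method only after seeing near-100% response would be post hoc.

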Listing 16.2.6.2.3 – Derived Primary and Secondary Efficacy Responses on Overall LFGS and Overall POL for Per-Protocol Population.....	80
Listing 16.2.6.2.4 – Derived Other Efficacy Responses Based on Observed Data: LFGS and POL for Upper/Lower Lip	81
Listing 16.2.7.1.1 – Adverse Events (Related to Vascular Injections/Visual Events).....	82
Listing 16.2.7.1.2 – Adverse Events (Excluding Vascular Injections/Visual Events).....	83
Listing 16.2.7.2.1 – Adverse Events (Related to Vascular Injections/Visual Events) Leading to Study Treatment Interrupted/Discontinued	83
Listing 16.2.7.2.2 – Adverse Events (Excluding Vascular Injections/Visual Events) Leading to Study Treatment Interrupted/Discontinued	83
Listing 16.2.7.3.1 – Serious Adverse Events (Related to Vascular Injections/Visual Events).....	83
Listing 16.2.7.3.2 – Serious Adverse Events (Excluding Vascular Injections/Visual Events).....	83
Listing 16.2.7.4 – Adverse Events (Related to Vascular Injections/Visual Events) Lasted more than 30 Days	83

Statistical Analysis Plan

1 Purpose of Statistical Analysis Plan

The purpose of the statistical analysis plan is to describe in detail all the data, statistical methods, and summary tables required to implement the statistical analysis of Clinical Study Protocol PRO 2018-02 (Section 8 in the study protocol version 4.0, dated October 02, 2018).

This plan has also incorporated responses to the FDA review comments on the Abbreviated SAP version 2.0, two consideration points in particular as follows:

- (1) Use of As-Treated (AT) population for safety instead of Intent-to-Treat population
- (2) For the primary efficacy endpoint, due to the likeliness that there will be a large number of ties in the ranked data, use the Wilcoxon Mann-Whitney test and the associated confidence interval for the median differences to test the non-inferiority hypothesis.

2 Study Objectives

To compare the safety and efficacy profile of PN40082 versus Restylane Silk Injectable Gel with 0.3% lidocaine (Restylane Silk) for lip augmentation.

3 Study Design and Sample Size Determination

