5.5 Efficacy Variables

Key efficacy assessments include the following:

- LFGS: 0 = very thin, 1 = thin, 2 = moderately thick, 3 = thick, 4 = full
- POL: 0 = None (a mouth with no perioral lines), 1 = Mild (a mouth with a few shallow perioral lines), 2 = Moderate (a mouth with some moderate lines), 3 = Severe (a mouth with many deep lines or crevices)
- Subject Satisfaction with Lips using a visual analog scale (VAS) on a 100-mm scale from 0 = Very Unsatisfied to 100 = Very Satisfied
- Patient Global Aesthetic Improvement (pGAI) Score: 1=Worse, 2=No change, 3=Improved, 4=Much improved, 5=Very much improved
- Investigator Global Aesthetic Improvement (iGAI) Score: 1=Worse, 2=No change, 3=Improved, 4=Much improved, 5=Very much improved
- Swelling Assessment: 0 = None, 1 = Minimal, 2 = Mild, 3 = Moderate, 4 = Severe

All efficacy analyses will be performed for both the PP and mITT populations.

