5.5.1 Primary Efficacy Analysis

The primary efficacy endpoint is change from baseline to Visit 3/Month 2 in overall LFGS. The null hypothesis to be tested is that the Test device is inferior to the Control device. The results for PP are considered as definitive and those for mITT as supportive.

Summary statistics (mean, SD, minimum, median, maximum) and 95% confidence interval (CI) for mean will be presented for the changes scores for each treatment.

Due to the fact that the change scores would only contain 5 possible values (0, 1, 2, 3, and 4), the normal distribution assumption is hardly attainable, and therefore, the nonparametric Hodges-Lehmann (HL) estimators will be employed to test the study hypothesis. The 95% confidence limits for the median differences between the two treatment groups (PN40082 minus Restylane Silk) will be derived using PROC NPARIWAY with the option for the HL estimators. If the lower limit is on or above -1.0, the null hypothesis will be rejected to support the claim that PN40082 is non-inferior to Restylane Silk.

For the mITT analysis, the above analysis will be carried out for each copy of the MI data sets. Then PROC MIANALYZE will be performed to account for the between and within variation in the multiply imputed data sets.

To assist an assessment for the consistency of the treatment effect among sites, summary of the primary endpoint will be presented by site for the primary population (i.e., the PP subjects).

The primary endpoint will also be analyzed for the following two subsets of the PP subjects: (1) subjects that have injection on one lip only, and (2) subjects that have injections on both lips.

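### For the Month 3 and Month 6 changes in lip fullness, the SAP replaces the protocol's ANCOVA with an unadjusted Hodges-Lehmann interval, without acknowledging the change and at a cost in resolution

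*SAP*

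**What the plan says.** Protocol 8.2 lists the overall LFGS changes to Month 3 and Month 6 as secondary endpoints and says that the 95% CI for the treatment difference will be "derived using ANCOVA with factors of treatment and site, and the corresponding baseline value for the endpoint as covariate".

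SAP 5.5.2 keeps the same two endpoints, ranked third and fourth of four, but says that "the 95% CI for the median differences between treatments will be derived using PROC NPARIWAY", using the Hodges-Lehmann option. No site or baseline term appears. The shell for Table 14.2.2.3, which also serves Table 14.2.2.4, carries this through: its only between-arm row is the median difference with its limits.

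The SAP gives two reasons for a rank method. Section 1 reports a point from the regulator's review that begins "For the primary efficacy endpoint, due to the likeliness that there will be a large number of ties in the ranked data". Section 5.5.1, on the primary analysis, adds that a change score with only five possible values cannot be expected to be normal. Section 5.5.2 gives no reason and does not mention that the ANCOVA has gone.

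Both documents call the secondary comparisons descriptive.

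**The concern.** The two methods estimate different things. ANCOVA gives a mean difference in grades, adjusted for site and baseline. Hodges-Lehmann gives the median of all between-arm pairwise differences, unadjusted. Replacing one with the other changes what is reported about how long the effect lasts, and a reader who holds the protocol is not told.

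The scale makes the change matter more. The grades are "LFGS: 0 = very thin, 1 = thin, 2 = moderately thick, 3 = thick, 4 = full". Every pairwise difference is therefore an integer, and so is each Hodges-Lehmann limit. With this many ties the two limits often coincide. A 95% interval of zero width reads as perfect precision, although the data remain compatible with a mean difference of a few tenths of a grade either way.

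The baseline term has a specific use here. Inclusion criterion 3 (Protocol 7.3.1) admits very thin or thin lips, and also thick or full lips in Fitzpatrick types IV to VI. Baseline scores can therefore sit at both ends of the scale: a subject at 4 cannot gain a grade, and one at 3 can gain only one. Protocol 7.4.2 mentions no stratification by baseline score or skin type.

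**Working it through.** **Inputs.** SAP 3.2 assumes "both PN40082 and Restylane Silk having an equal mean value with a common standard deviation of 0.85", "the non-inferiority limit of -0.50", 63 per-protocol subjects per arm and 90% power. Protocol 8.5 inflates this to 79 per arm, assuming that 80% qualify. Neither document gives an SD by visit, so 0.85 is assumed for both Month 3 and Month 6.

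**The plan's own figure.** n per arm = 2 × 0.85² × (1.960 + 1.282)² / 0.50² = 60.7, so 61. A t-based calculation needs 62. The stated 63 gives 91.0% power (normal) or 90.6% (t), and 126 / 0.8 = 157.5, so 158. The sizing is reproduced to within two subjects per arm.

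**When the interval collapses.** The large-sample Hodges-Lehmann limits are the pairwise differences at rank C from each end:

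C = mn/2 − 1.96 × √(mn(m + n + 1)/12)

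With m = n = 63: C = 1984.5 − 1.96 × √(3969 × 127/12) = 1984.5 − 401.7 = 1582.8.

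1582.8 / 3969 = 39.9%. The interval is therefore (0, 0) whenever fewer than about 40% of pairs favour either arm.

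As an illustration, let both arms have changes of −1, 0, 1, 2 and 3 with probabilities 0.03, 0.24, 0.46, 0.24 and 0.03:
- The variance is 2 × (0.24 + 4 × 0.03) = 0.72, so the SD is 0.85.
- The tie probability is 0.46² + 2 × 0.24² + 2 × 0.03² = 0.329.
- Each side then has (1 − 0.329)/2 = 33.6% of pairs, well below 39.9%.

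Collapse is the expected result in this case.

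**Simulation.** Integer changes were drawn from a discretised normal with mean change 0.5 to 2.0, 3,000 trials per setting, without tie correction. The shape of the distribution is an assumption. Proportion of trials with interval exactly (0, 0):

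| Per arm | SD | True difference | Interval is (0, 0) |
|---|---|---|---|
| 63 | 0.70 | 0 | 95–96% |
| 63 | 0.85 | 0 | 78–81% |
| 63 | 1.0 | 0 | 53–57% |
| 63 | 1.1 | 0 | 34–38% |
| 63 | 0.85 | −0.1 | 69–72% |
| 63 | 0.85 | −0.2 | 49–51% |
| 63 | 0.85 | −0.25 | about 37% |
| 63 | 0.85 | −0.3 | 24–27% |
| 79 | 0.85 | 0 | 89–91% |
| 79 | 0.85 | −0.2 | 57–60% |

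In the equal-arm case almost all other intervals are (−1, 0) or (0, 1). At a true difference of −0.5 the usual result, in about 94% of trials, is (−1, 0). A tie-corrected variance raises the equal-arm figure at SD 0.85 to 83–85%. At a deficit of 0.2 grade, moving from 63 to 79 per arm makes (0, 0) more likely, not less.

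**What a mean-difference interval would show.** The unadjusted half-width at 63 per arm is 1.96 × 0.85 × √(2/63) = 0.30. Multiplying by √(1 − r²) gives 0.28 for a baseline correlation of 0.3 and 0.26 for 0.5. These correlations are assumed; the documents give none.

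**The case against.** The strongest reply is that little depends on this. The endpoints are descriptive, and the table shells also print each arm's N, mean, SD, 95% CI of the mean, median and range. A reader might infer from the point above that durability would be reported only as a difference of 0 (0, 0). The documents do not support that: a 0.25-grade gap would be visible in the adjacent means, and an unadjusted interval for the difference could be worked out from the printed rows. This stands, and it sets the priority.

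A reader might also infer that the SAP's method would conceal a clear deficit. It would not. At a deficit of 0.25 grade most trials give an interval other than (0, 0). The mean-difference interval would not reliably detect that deficit either: its SE is 0.85 × √(2/63) = 0.151, so it excludes zero with probability about Φ(0.25/0.151 − 1.96), or 37–38%. Even with an assumed baseline correlation of 0.5 the figure is about 48%. The loss is one of resolution.

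The argument that the change score is far from normal applies to the same scale at later visits, so extending the rank method is not arbitrary. The regulator's full comments are not in the documents, so it cannot be said that they left the secondary endpoints untouched. Still, the SAP records no such reason. Protocol Section 8 expects the SAP to explain the methods more fully, which an unmarked replacement does not do.

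Finally, ANCOVA alone at Months 3 and 6 beside Hodges-Lehmann at Month 2 would make the visits harder to compare. That is a fair objection to dropping the Hodges-Lehmann line, but not to adding the ANCOVA line.

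**Conclusion.** The discrepancy is plain on the page and unexplained: an adjusted mean difference in Protocol 8.2, an unadjusted median of pairwise differences in SAP 5.5.2 and its tables. Under the plan's own inputs the SAP's interval is exactly (0, 0) in about four trials in five, where the protocol's would have a half-width of at most about 0.30 grade.

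That frequency depends on near-equal arms and an SD near 0.85. It is about 55% at SD 1.0, about 37% at a 0.25-grade deficit with SD 0.85, and lower beyond that. A reader might take (0, 0) to be the usual result whatever the data; the figures do not support that, and the SD at Month 3 and Month 6 is not given.

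The gain from baseline adjustment is modest on the correlations tried (0.30 down to 0.28 or 0.26). The main loss is the missing between-arm interval on the mean scale. No claim of non-inferiority rests on these endpoints, so this is a low-priority point.

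**What to change.** In SAP 5.5.2 and Tables 14.2.2.3 and 14.2.2.4, restore the protocol's ANCOVA (treatment, site, baseline) and report the adjusted mean difference with its 95% CI. For the mITT population, pool it across the imputed data sets; the ANCOVA estimate comes with the standard error that this step needs. Keep the Hodges-Lehmann line beside it, so that Months 3 and 6 can be read against Month 2. Add a sentence saying why both are shown.

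The cost is SAP wording, one extra table row per analysis and a short piece of code. The model is already in the protocol, and no new data, visits or subjects are needed. This is a free improvement.
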